To avoid bias in selecting the final regression model for the risk adjusted analyses of the nonrandomized patients, the baseline predictors will be determined before the logistic regression analyses are performed. Selection will be based on biologic plausibility, the results of our prior observational study, and univariate analyses of trial results. Likewise the baseline variables used in the final models for propensity scoring will be determined before any of these analyses are performed. Diagnosis & prognosis will be assessed using methods developed in our prior observational study. Nominal p values will be calculated for secondary outcomes without adjustment for multiple comparisons. Exploratory subgroup differences will be performed.

We plan to collect the same data for eligible, non-randomized infants (with consent) as for randomized infants. This will allow comparison of the patient characteristics and outcomes in the randomized and non-randomized cohorts and perhaps assess the external validity of our study findings (generalizability). As a secondary analysis, the risk adjusted relative risk will be determined in the randomized & preference groups and the value of combining these cohorts will be evaluated. This approach, known as a comprehensive cohort design, has been recommended in a recent meta-analysis for rare diseases or for evaluation of emergency therapies.¹⁰ Whether this approach is useful or not will be a secondary aim and these analyses will not affect the primary analysis of the randomized cohort.

Currently, there is unavoidable uncertainty about differences between the Bayley II and III outcomes. Based on Network GDB data available at this time, it appears that a Bayley III score <85 best approximates that of a Bayley II <70 which has been previously used by the Network in the definition of neurodevelopmental impairment. As this trial progresses, an increasing body of data will accumulate regarding the differences in

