For cases where we don't have enough information from the follow up visit to assign a level of NDI, adjudication will be performed. In most cases this happens when the Bayley score is missing and the other components are negative. For such situations, we will convene a subcommittee, and asked them to review the neurologic assessment and follow up visit assessments for each of these babies in a blinded fashion (no treatment group) to determine if they can discern, based on all the available information, whether:

- (a) NDI is likely present,
- (b) NDI is likely absent, or
- (c) NDI cannot be determined.

Once adjudication is complete, we will conduct the primary and affected secondary analyses incorporating this information (treating the last category as missing data). In addition to this analysis, sensitivity analyses will be completed to determine whether the adjudicated outcomes change any results.

Appropriateness of Primary Target Variable

Until recently, all studies evaluating laparotomy and drainage have focused on death and other outcomes occurring in the immediate post operative period. An editorial in the New England Journal of Medicine pointed out the limitations of current studies evaluating surgical therapies in NEC and highlighted the importance of measuring neurodevelopmental outcome beyond nursery discharge. The previously completed observational study by the Network is the only prospective study addressing neurodevelopmental outcome in addition to death at a long-term time point such as 18-22 months.

Results from the Network's observational study suggested that laparotomy may improve long term outcome as measured by death or NDI (risk adjusted odds ratio for death or disability (0.55; 95% CI= 0.18 – 1.67), so the NEST subcommittee considered it very important to study death and NDI at a time point beyond discharge.

Secondary Target Variables

Secondary outcomes variables will include surgical complications,

- such as wound dehiscence, (**variable name is Patient.wound_dehis**)
- intestinal stricture or fistula, (**variable name is Patient.intest_strict and Patient.Fistula**)
- procedure-related liver hemorrhage, (**variable name is Patient.LiverHemorrhage**)
- number of surgical procedures, (**variable name is Patient.TotalSurgeries**)
- sepsis episodes, (**variable name is Patient.GDB_SEPSIS**)
- duration of parenteral nutrition, (**variable name is Patient.GDB_PARDAYS**)

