The primary analysis of randomized cohort data will assess the effect of treatment on death or NDI at 18-22 months corrected age, death, and other clinical outcomes as defined in Study Endpoint section above (pages 8-10) and listed on pages 13 and 14. This analysis will be performed using a robust Poisson regression model identical to the model defined on page 17 and 18. If possible center will also be included in the model as a fixed or random effect. The default will be a fixed effect, but a random effect may be used if model convergence issues results from using a fixed effect. The outcome variable will assign one to the event of death or NDI at 18-22 months corrected age and zero otherwise. The treatment variable will assign one to laparotomy and zero to drainage. It follows that relative risks less than one (or less than zero on the log scale) will favor Laparotomy.

Like the efficacy interim analysis, the final test statistic produced for the treatment effect will be a z-statistic. This z-statistic will be compared to the appropriate boundary pair calculated from the updating call to `gsDesign()` as described in the efficacy interim analysis section. As with the interim efficacy analyses, the actual robust regression modeling at each interim analysis will be completed in SAS, and a figure summarizing the final analysis results will be constructed in Excel. This figure will contain information from all prior interim efficacy analysis results.

In addition to the above formal adjusted analyses, simple unadjusted treatment comparisons of randomized data will be completed, and 95% confidence intervals of differences in proportions will be constructed. The formatting of these tabulations will be determined as the corresponding papers develop.

Secondary Analysis of Primary Outcome Using Randomized Cohort Data

The analyses will include an assessment of whether there is an interaction between treatment (laparotomy or drainage) and disease (NEC or IP). This assessment will use a robust Poisson regression model with will include treatment (laparotomy or drainage), preoperative diagnosis (NEC or IP), and the treatment by preoperative diagnosis interaction. If the Wald test for the interaction term has a p-value less than 0.05, then the conclusion will be the study has produced evidence of an interaction between treatment and pre-operative diagnosis with respect to the primary outcome. If such

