evidence is produced, we will produce treatment effect estimates separately for NEC and IP.

The same robust Poisson regression model will be used to compare treatment with respect to death and other secondary outcomes as mentioned on page 20.

Because NDI adjudication is used, analyses of the primary outcome and analysis of any NDI conditional on survival will include sensitivity analyses to determine whether the adjudicated outcomes change any results. Such sensitivity analyses will include removing all babies with adjudicated outcome for the analysis, switching the value of the adjudicated, and if possible, imputing the NDI based on a predictive model of NDI conditional on survival. Since this predictive model will be exploratory, the details of how this predictive model will be build are not defined in this SAP.

Bayesian Analysis of Primary Outcome using Randomized Cohort Data

R and WinBUGS or JAGS software will be used to analyze the final data from a Bayesian perspective. A Bayesian model contains three components: a model or *likelihood* for the data, a *prior* distribution embodying beliefs or historical knowledge regarding the model parameters before new data are observed, and the posterior distribution embodying updated belief probabilities regarding the model parameters and/or functions of the model parameters after the new data are observed.

The outcome from the i^{th} infant used in the model will be:

$$y_i = \begin{cases} 0 & \text{for survival without NDI} \\ 1 & \text{for death or survival with NDI} \end{cases}$$

The covariates will have the form:

$$s_i = \begin{cases} 0 & \text{initial surgery was drain} \\ 1 & \text{initial surgery was laparotomy} \end{cases}$$

$$r_i = \begin{cases} 0 & \text{low baseline risk for death or NDI} \\ 1 & \text{high baseline risk for death or NDI} \end{cases}$$

The model will have the form:

$$y_i | (s_i, r_i, c_i) \sim \text{Bernoulli}[\pi(s_i, r_i, c_i)] \text{ where}$$

$$\log[\pi] = \alpha_c + \vartheta \cdot s_i + \gamma \cdot r_i \text{ and } c \text{ represents the site for the } i^{\text{th}} \text{ infant among } C \text{ total sites.}$$

$$c \sim N(0, \sigma_c^2)$$

Note that this model differs from the primary analysis model in that it is a log-binomial model and center is included in the model as a random effect.

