Estimates of baseline risk adjusted relative risk on the log scale and the standard errors will be estimated from the robust Poisson regression models. The variance for the estimated baseline risk adjusted relative risk on the log scale will equal the square of the standard error calculated from the sandwich estimator.

Statistical Appendix A: Exploratory Analysis for Statistician's benefit (will be completed only after all publication required analyses are completed.)

Interestingly, bootstrap analysis of a binary outcome using Poisson regression, when the outcome is a function of treatment, produces an empirical distribution of estimated relative risk on the log scale that is approximated by a normal distribution. Also, an empirical 95% confidence interval for the relative risk on the log scale calculated from these bootstrap samples will approximate a 95% confidence interval for the relative risk on the log scale calculated for a robust Poisson regression model.

For example, using simulated data containing a binary outcome which is a function of treatment and a two level strata variable, the following results occurred:

- The estimated $\log(\text{RR})$ using a robust Poisson regression model was -0.209, compared to the true value of -0.208.
- The 95% CI for the treatment effect on the $\log(\text{RR})$ scale using robust Poisson regression was -0.347 to -0.071.
- The estimated median bootstrap estimate of $\log(\text{RR})$ using Poisson regression was -0.209, based on 10000 bootstrap samples.
- The 95% CI for the treatment effect on the $\log(\text{RR})$ scale using the bootstrap estimates was -0.356 to -0.078.

Also, Figure 1 shows that the 10,000 bootstrap estimates of $\log(\text{RR})$ from the Poisson regression does approximate a normal distribution.

[figure not shown]

Figure 1

The program used to study the relation between robust Poisson regression and bootstrapped Poisson regression of a binary outcome is included in Statistical Appendix B.

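### The robust Poisson test planned for all secondary outcomes gives a spuriously tiny p-value when exactly one arm has no events, and the SAP has no rule for that case

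*SAP*

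**What the plan says.** Under Final Analyses, the SAP's section on the primary analysis of the randomized cohort applies the robust Poisson model to death or NDI and also to "death, and other clinical outcomes as defined in Study Endpoint section above (pages 8-10) and listed on pages 13 and 14". The next section, on secondary analysis of the primary outcome, repeats this: "The same robust Poisson regression model will be used to compare treatment with respect to death and other secondary outcomes". The model contains treatment, baseline risk and, if possible, center. On the test, the SAP says that "the final test statistic produced for the treatment effect will be a z-statistic". The section on combining the cohorts shows which variance goes with these models: "the square of the standard error calculated from the sandwich estimator".

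The SAP's Secondary Target Variables include wound dehiscence, stricture, fistula, "procedure-related liver hemorrhage", and the separate NDI components, among them blindness and deafness. The Protocol (Statistical Analyses) adds: "Nominal p values will be calculated for secondary outcomes without adjustment for multiple comparisons".

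The only fallback for a fitting problem is to move center from a fixed to a random effect. Fisher's test appears only in the sample-size calculation and in the comparison of baseline-risk distributions at interim looks. Alongside the model, the SAP promises that "simple unadjusted treatment comparisons of randomized data will be completed, and 95% confidence intervals of differences in proportions will be constructed". It names neither the test nor the interval method for these comparisons.

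**The concern.** A Wald test needs an estimate and a standard error that both mean something. With an empty arm, the maximum-likelihood log relative risk is infinite and the software stops wherever its convergence rule tells it to. An ordinary model-based standard error would be in the thousands and would give p near 1, so the failure would be harmless. The sandwich standard error stays small, so the ratio looks like overwhelming evidence.

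At stake is the reporting of uncommon harms and sensory outcomes. Applied as written, the plan would attach a near-zero nominal p-value to a difference of one, two or three infants. If the anomaly is noticed, the replacement method would be chosen after the data are seen, by a statistician whom the SAP describes as unmasked.

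**Working it through.** **The plan's own figure.** The SAP (interim efficacy section) gives 80% power by Fisher's exact test with 150 per arm, 80% v 65%, and 82% by simulation with robust Poisson and the interim looks. Full enumeration of the two-sided Fisher test gives 80.3%. A 6,000-run simulation of robust Poisson (treatment and risk) with bounds 4.05, 2.86, 2.34 and 2.02 gives 83.1%. Both agree with the plan. The model is sound for the common primary outcome; the question is only what it does with an empty arm.

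**Inputs.** 150 per arm (Protocol and SAP). For follow-up components, 144 assessed survivors (Protocol, Sample Size), or 144/2 = 72 per arm if split equally. 16 centers (Protocol, Sample Size). The event rates are assumptions.

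**Why the standard error stays small.** In an arm of n infants with no events, every residual is −μ, where μ is the fitted mean. The sandwich variance of that arm's log rate is nμ²/(nμ)² = 1/n, however small μ becomes. The other arm, with k events, contributes (1 − k/n)/k = 1/k − 1/n. The sum is 1/k, so SE = 1/√k: 1.00, 0.71 and 0.58 for k = 1, 2 and 3.

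**Fits at 150 per arm, treatment-only model, convergence tolerance 1e-8:**

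| Events | SE | z | Model p | Fisher p |
|---|---|---|---|---|
| 1 v 0 | 1.00 | 17.7 | about 5e-70 | 1.00 |
| 2 v 0 | 0.71 | 25.0 | about 4e-138 | 0.50 |
| 3 v 0 | 0.58 | 30.6 | about 3e-206 | 0.25 |

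With risk added and a standard GLM routine at its default settings, 1 v 0 gives log RR 21.0, SE 0.99 and p about 1e-99, with convergence reported. The exact p is set by the tolerance. At a loose 1e-4, 2 v 0 still gives log RR 8.69 in absolute value, z = 12.3 and p about 1e-34.

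**With 16 center fixed effects.** A generalised-inverse fit gave p < 0.001 in 200 of 200 runs for each of k = 1, 2, 3 and 5. A standard routine gave p about 1e-184 for k = 2 and failed for k = 3 and k = 5. The SAP does not say what is reported after such a failure. SAS, the software named in the SAP, was not tested.

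**How often exactly one arm is empty when the true rates are equal.** With q = (1 − p)^n, the chance is 2q(1 − q).

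| Assumed rate | q (n = 150) | n = 150 | n = 72 |
|---|---|---|---|
| 0.5% | 0.4715 | 50% | 42% |
| 1% | 0.2215 | 34% | 50% |
| 2% | 0.0483 | 9% | 36% |
| 3% | 0.0104 | 2% | 20% |
| 5% | 0.0005 | 0.1% | 5% |

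At 150 per arm, the overall false-positive rate of the treatment-only test at nominal 5% is 50%, 35%, 9.6%, 3.4% and 3.1% at these five rates. Nearly all of the excess comes from empty arms. Fisher's test stays at or below 3.3% for rates from 0.33% to 10%.

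**With at least one event per arm**, the artefact disappears:

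| Events | Model p | Fisher p |
|---|---|---|
| 1 v 3 | 0.34 | 0.62 |
| 1 v 6 | 0.095 | 0.12 |
| 4 v 15 | 0.016 | 0.016 |

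**The case against.** The strongest reply is that no one would be misled. The SAP also plans unadjusted comparisons with intervals for the risk difference, and for 1 to 3 events v 0 these include zero (3 v 0: Wald −0.2% to 4.2%, Newcombe −0.8% to 5.7%). A relative risk of around a billion beside counts of 1 v 0 would be noticed. Secondary p-values are nominal, the trial was powered for the primary hypothesis only, and no claim rule is attached to any secondary outcome.

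Most of this stands. A reader might infer that rare complications would be published as highly significant. The documents do not support that, because the planned intervals would sit beside the model result and contradict it. What remains is that those comparisons are additional to the formal adjusted analysis, and the SAP does not say which result governs.

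A reader might also infer that Secondary Hypothesis 3 rests on these tests. It speaks of the proportion of infants with surgical complications and gives examples, so it can be read as an any-complication proportion, for which an empty arm is far less likely. Nor do the documents show that liver hemorrhage, fistula, blindness or deafness is rare enough to be affected. The cause-of-death categories belong to an interim list tabulated without p-values. They reach the final model only through a page reference that cannot be checked in the text available.

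**Conclusion.** The concern holds in a limited form. For any binary secondary outcome with events in one arm only, the specified analysis gives a wrong p-value, not merely an imprecise one. The mechanism follows from the algebra and was confirmed in fits with and without center, although some center fits failed outright and SAS was not run.

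How often this would arise depends on event rates that the documents do not give. At 150 per arm it is a serious prospect at rates of 1% or below, modest at 2% and negligible at 5%. With 72 per arm it extends to somewhat higher rates. The calculation assumes equal true rates and equal arms.

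The primary analysis is unaffected. A reader might infer that the model should be dropped for sparse outcomes generally, for example below five events in an arm. The figures do not support that: 1 v 6 and 4 v 15 give sensible results, and such a rule would discard the planned adjustment without need.

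**What to change.** Add to the SAP section on secondary analysis, directly after the sentence extending the model to death and the other secondary outcomes:

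> For any binary secondary outcome with no events in one treatment arm, the robust Poisson estimate and p-value will not be reported; counts, Fisher's exact p and an exact confidence interval for the risk difference will be given instead.

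This also settles what is reported if an empty arm makes a center-adjusted fit fail. The cost is one sentence, plus the loss of adjustment for risk and center for those outcomes only.

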
Analysis & Interpretation. The primary outcome (death or NDI at 18-22 months corrected age) will be analyzed in standard logistic regression equations in which the predictor variables include center, and level of risk at enrollment as determined by the method described above. Separate analyses will be used to assess whether there is an interaction between treatment (laparotomy or drainage) and disease (NEC or IP). Secondary analyses of randomized patients will be performed using Bayesian methods to assess the (posterior) probability that laparotomy reduces death or NDI relative to that with drainage.

Consent to randomization may be unobtainable before surgery for a sizable proportion of infants. Providing parents at least agree to collection of the same baseline and outcome data as for randomized infants, we will relate surgical treatment to risk adjusted outcome. A finding that the risk adjusted relative risk in the nonrandomized patients is similar to the relative risk observed in the randomized patients will support the validity of the trial results and generalizability of the results among randomized patients to nonrandomized patients. (This would be expected based on a prior meta analysis of studies using a comprehensive cohort design [JAMA 2005]). Whether use of propensity scoring also supports the results among randomized patients will also be assessed.

Sample Size and Resources. Based on our observational study, we hypothesize that 80% of drain infants and 65% of the laparotomy infants will die or be impaired (NNT = only 7 to gain one unimpaired survivor); 300 infants (150 / group) whose primary outcome is determined will be needed (alpha =0.05 & beta = 0.20, two sided Fisher exact test). Enrollment will likely require 4 years (assuming a consent rate of 50%) unless the consent rate is higher than projected. We propose to initiate this trial within Network sites initially given the importance and urgency of the clinical question. Enrollment will be prospectively monitored and if found to be low after 6 months (after 80% of participating centers have IRB approval and are actively participating in the trial), consideration will be given to add additional sites. Despite the difficulties anticipated with the proposed trial, the total expense and effort required will be small relative to other Network trials, and the trial may facilitate future trials involving urgent/emergent therapies, rare diseases, or surgical interventions.

TRIAL OBJECTIVES

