6. Develop improved methods to define the prognosis of individual infants presenting with signs of NEC or IP.
7. Provide information that would be deemed useful by the subcommittee for any other simultaneous clinical trials.

Finally, the protocol extracts the following hypotheses from the above objectives and specific aims.

Primary Hypothesis

1. Initial laparotomy rather than drainage will result in a higher rate of survival without NDI at 18-22 months adjusted age among ELBW infants presented with signs of NEC or IP.²

¹ The risk stratification formula was primarily developed in a prospective observational study of NEC previously conducted by the NRN and includes the following variables: birth-weight, gestational age, vasopressor requirement (yes/no), if infant is on high frequency (oscillating or jet) ventilation or not (any modality of conventional ventilation or no mechanical ventilation), pH, FiO₂, and preoperative diagnosis (NEC or IP).

Secondary Hypotheses

1. The generalizability of the results in randomized patients to nonrandomized patients will be supported by analyses using conventional risk adjusted relative risk among nonrandomized patients (as in a comprehensive cohort design) and by analyses using propensity scoring.
2. The laparotomy group will have a similar or better outcome than the drainage group with respect to other outcomes during the neonatal period (death; death or prolonged parenteral nutrition; death or prolonged hospital stay) and at follow-up (e.g. each component of NDI; anthropometry).
3. The proportion of infants who have surgical complications (e.g. procedure-related liver injury, wound dehiscence, intestinal stricture or fistula) will be similar in the two treatment groups.
4. There will be no significant statistical interaction between treatment and diagnosis.³
5. The trial data will provide improved methods to distinguish ELBW infants with NEC from those with IP.
6. The trial data will provide improved methods to assess the prognosis of ELBW infants presenting with signs of NEC or with IP.

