- parenteral nutrition associated cholestasis, (**variable name is Patient.PN_assoc_chol**)
- length of hospital stay, (**variable name is Patient.GDB_HOSPSTAY**)
- rehospitalizations, (**variable name is Patient.?**)
- each component of the primary outcome;
 - Cerebral Palsy classification (GMFCS Level ≥ 2) [**classification variables are Patient.GMFCS_GTE2 and Patient.Any_CP, while the raw variable for GMFCS is Patient.EFGROSS.**]
 - BSID III score (Bayley III Cognitive score < 85) [**classification variable is Patient.LowBayley, while the raw variable is Patient.NF9ABSCC.**]
 - Vision assessment (< 20 - 200 vision or legally blind) [**classification variable is Patient.BILATERAL_BLINDNESS, while the raw variables are Patient.EFVISNL and Patient.EFVISNR.**]
 - Hearing assessment (permanent hearing loss) [**classification variable is Patient.DEAF, while the raw variable is Patient.EFHEARIM.**]

Study Methods

Overall Study Design and Plan

Similar to a Comprehensive Cohort Design, the study design is an unmasked randomized trial accompanied by a nonrandomized cohort. Data from the nonrandomized cohort will be analyzed and results compared to similar results derived from analyses of randomized cohort data. Covariate adjustment methods, and propensity scores will be utilized in an attempt to adjust for selection bias in the nonrandomized cohort. The nonrandomized cohort is not a representative sample of all eligible infants not randomized, but it is a sample of eligible infants whose surgeon, neonatologist, or parents refused randomization. If the results from properly adjusted analyses of nonrandomized cohort data are similar to the results from the analyses of randomized cohort data, then we have some evidence for the generalizability of the randomized cohort results. On the other hand, if important differences do occur, then differences will need to be explained using reasonable arguments not grounded in statistical theory but clinical understanding. Enrollment into the nonrandomized cohort was terminated on February 14, 2013.

Selection of Study Population

Inclusion Criteria:

1. birth weight of $\leq 1,000$ g,
2. a decision by the attending pediatric surgeon to perform surgery for suspected NEC or IP (The indications for surgery for infants with NEC or IP vary among surgeons and sites),
3. the infant is less than or equal to 8 weeks of age (8 0/7 weeks or less) at the time of eligibility assessment, and

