The treatments in this trial will be conducted during the first few weeks of life for most study subjects, while the primary outcome of death or neurodevelopmental impairment will be assessed at 18-22 months of age. As a consequence, to ensure the safety of participants and trial integrity, interim analysis will be completed using both safety and efficacy data but an emphasis will be placed on adverse events and other safety measures.

The interim analysis plan described below ensures that adverse events are monitored more frequently than measures of efficacy, and the statistical bounds used to detect group differences in adverse event rates are more liberal than those used to determine efficacy. The safety monitoring will consist of summary adverse event tables and a mortality monitoring scheme that uses Pocock type sequential testing boundaries. The scheme for monitoring the primary efficacy variable will use Lan-DeMet's spending functions to implement O'Brien-Fleming type boundaries while accounting for unequally spaced interim analyses. Lan-DeMet's spending functions will be used to estimate the boundaries at each interim efficacy analysis, because we cannot precisely predict beforehand what proportion of trial enrollees will have primary outcome data available before each of the annual DSMC meetings.

Adverse events during the course of the trial treatment period will be prospectively monitored, as will clinical morbidities throughout hospitalization. The enrolled population is extremely high risk, and their hospitalization can produce a great number of expected adverse events and clinical diagnoses. Rates of these events, historically observed among similar extremely low gestation/birth weight infants, will be provided to the DSMC.

The set of clinical outcomes monitored were:

- Death
- Number of surgeries
- Surgical complication
- Parenteral alimentation
- Days on parenteral alimentation
- Days in hospital
- Severe IVH
- PVL
- Seizures
- PDA prior to enrollment
- PDA treated
- EOS
- LOS
- ROP
- BPD

- Death or serious morbidity (Hosp.)
- Death or Severe IVH
- Death or sepsis
- Death or ROP
- Death or BPD
- Causes of Death
 - CNS insult
 - Gastrointestinal
 - Immaturity
 - Infection
 - Malformation
 - Pulmonary
 - Other

For each of the above conditions, summary tables will tabulate counts by treatment group and cohort, but these summaries will not include inferential statistics such as p-values or confidence intervals.

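### NDI and its components are compared among survivors only, with nothing to handle selection by death; the primary composite is unaffected, but these secondary comparisons are not protected by randomization

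*SAP*

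**What the plan says.** - **NDI given survival.** The SAP section on secondary analysis of the primary outcome states that "analyses of the primary outcome and analysis of any NDI conditional on survival will include sensitivity analyses". Those sensitivity analyses remove, switch or impute the adjudicated outcomes.
- **Components.** The SAP's Secondary Target Variables include "each component of the primary outcome": CP by GMFCS level, Bayley III cognitive score below 85, vision and hearing. No denominator is given.
- **Treatment claim.** Secondary Hypothesis 2 expects laparotomy to be similar or better "at follow-up (e.g. each component of NDI; anthropometry"). The Protocol's Statistical Analyses section gives secondary outcomes nominal p-values.
- **Model.** "The same robust Poisson regression model will be used to compare treatment with respect to death and other secondary outcomes".
- **Primary outcome.** "The outcome variable will assign one to the event of death or NDI at 18-22 months corrected age and zero otherwise".
- **Pairing with death elsewhere.** Secondary Hypothesis 2 combines prolonged parenteral nutrition and prolonged hospital stay with death. The monitored outcomes under Interim Analyses include "Death or Severe IVH" and matching pairs for sepsis, ROP and BPD, and the final-analysis section appears to carry that list forward by page reference. The 18-22 month components have no such pairing.

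**The concern.** Randomization balances the infants who enter the trial, not those alive at 18-22 months. The Protocol plans on about half of each arm dying. If one procedure keeps alive some infants who would have died under the other, and those infants are more often impaired, the survivor-only RR mixes the effect on neurodevelopment with a change in who is assessed. The arm with better survival then looks worse on impairment than it truly is. Equal numbers of survivors do not settle the matter if different kinds of infants survive.

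The components matter for interpretation. At the planned equal mortality, the whole hypothesized benefit runs through impairment among survivors, so readers will turn to the component results to explain the primary one. The SAP gives no caveat and no companion analysis for that step.

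**Working it through.** **1. The plan's own figures.** The Protocol states "300 infants (150 / group) whose primary outcome is determined will be needed (alpha =0.05 & beta = 0.20, two sided Fisher exact test"), on the hypothesis that "80% of drain infants and 65% of the laparotomy infants will die or be impaired". This reproduces: exact enumeration of the two-sided Fisher test at 150 per arm gives 80.3% power. The accrual arithmetic also holds: 160 × 0.50 × 4 = 320 enrolled, then 160 deaths + 0.90 × 160 = 144 assessed survivors, 304 in total.

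**2. Implied NDI among survivors.** With the planned 50% mortality in each arm:
- Drain: (0.80 − 0.50)/0.50 = 60%
- Laparotomy: (0.65 − 0.50)/0.50 = 30%

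**3. Mortality inputs for an illustration.** The Protocol's review of subsequent laparotomy reports, for the UK randomized trial, 36% mortality with laparotomy, 49% with drain only and about 42% with drain plus later laparotomy. Of 35 drain infants, 26 had a later laparotomy and 9 did not.
- Label taken literally, the drain-arm blend is (9 × 49% + 26 × 42%)/35 = 43.8%.
- The label is doubtful: 4/9 = 44% and 5/9 = 56%, so 9 infants cannot give 49%, whereas 17/35 = 48.6% can. Both readings are carried below.

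**4. Formula.** Assume surgery has no effect on neurodevelopment, and every infant who would survive with a drain would also survive with laparotomy. Let S_D and S_L be survival by arm, b the NDI rate in infants who survive either way, and q the rate in those saved only by laparotomy.

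Laparotomy survivor NDI = [S_D × b + (S_L − S_D) × q]/S_L

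Spurious RR = 1 + [(S_L − S_D)/S_L] × (q/b − 1)

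The RR is 1 if S_L = S_D (under the survival assumption above, the same infants then survive in both arms) or if q = b.

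**5. Results with b = 50% (assumed) and S_L = 0.64.**

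| Drain mortality | q | NDI, laparotomy survivors | Spurious RR | Death or NDI, drain vs laparotomy |
|---|---|---|---|---|
| 43.8% | 50% | 50.0% | 1.00 | 71.9% vs 68.0% |
| 43.8% | 70% | (0.281 + 0.0546)/0.64 = 52.4% | 1.05 | 71.9% vs 69.6% |
| 43.8% | 80% | (0.281 + 0.0624)/0.64 = 53.7% | 1.07 | 71.9% vs 70.3% |
| 49% | 50% | 50.0% | 1.00 | 74.5% vs 68.0% |
| 49% | 70% | (0.255 + 0.091)/0.64 = 54.1% | 1.08 | 74.5% vs 70.6% |
| 49% | 80% | (0.255 + 0.104)/0.64 = 56.1% | 1.12 | 74.5% vs 71.9% |

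The survivor-only RR moves against laparotomy although no infant is harmed, while death-or-NDI moves in its favor.

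**6. Other inputs.** With b = 60%, as implied in step 2, and q = 80-100%, the RR is 1.07-1.14 at 49% drain mortality and about 1.04-1.08 at the blend. A real benefit would be diluted: at 49% vs 36%, a true RR of 0.75 in infants who survive either way (60% to 45%) appears as [(0.51 × 0.45 + 0.13 × 0.80)/0.64]/0.60 = 0.87 with q = 80%, and 0.94 with q = 100%.

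**The case against.** - **The primary inference is safe.** The composite counts death as an event in all randomized infants, and death is also compared separately, so a survival gap would be visible beside any survivor-only figure. The SAP says the trial was powered for the primary hypothesis only. This stands. A reader might infer that the primary result is biased; the documents do not support that.
- **A survival gap is not expected.** The Protocol plans 50% mortality in each arm and cites equivalent survival in earlier studies. It reports no significant differences among the UK trial's subgroups. This stands as a limit on size. A reader might infer that laparotomy will appear harmful; the documents establish neither a mortality difference nor a higher NDI rate in extra survivors.
- **The model adjusts for baseline risk.** The high/low stratum, and center where possible, absorb part of a difference in fragility, and the illustration is crude. A binary stratum cannot be relied on to remove it all.
- **The bias is small against the noise.** With 72 assessed survivors per arm and 50% NDI, the standard error of log RR is √(2 × 0.5/(72 × 0.5)) = 0.167, so 95% limits are about ×/÷ 1.39. An RR of 1.12 is log 0.113, about 0.7 standard errors. This is fair, but nominal p-values will still be attached.
- **The survivor denominator for components is inferred.** The SAP does not state it, and the data dictionary is not in the documents. But the components are measured only at follow-up, and coding dead infants as zero would count death as a good result. Either way the text needs to say.
- **Death-or-component outcomes are blunt.** At 50% mortality, deaths would swamp vision and hearing. This stands, and it argues against replacing every component comparison.

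**Conclusion.** The concern holds for the secondary comparisons of NDI and its components. They are conditioned on survival, explicitly for any NDI and by the timing of assessment for the components, and nothing in the plan addresses selection by death. The spurious RR is modest: about 1.05-1.07 or 1.08-1.12 under the two readings of drain mortality, against 36% with laparotomy. These figures rest on assumed NDI rates of 50% and 70-80% and on no true neurodevelopmental effect. The distortion is nil if extra survivors carry no extra risk or the same infants survive in both arms. It may dilute a true benefit rather than reverse it. The primary composite and the death analysis are unaffected. This is a worthwhile correction to the secondary analyses, not a flaw in the main test.

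**What to change.** In the SAP's Secondary Target Variables and its section on secondary analysis of the primary outcome:

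1. State that the denominator for any NDI and each component is assessed survivors.
2. Present those survivor-only comparisons as descriptive, beside death and death-or-NDI, with a note that they are not randomized comparisons.
3. Add death-or-component outcomes in all randomized infants with the same robust Poisson model, at least for moderate/severe CP and Bayley III below 85.
4. Add a table by arm of dead, alive with NDI and alive without NDI.

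The cost is SAP wording and a few table rows; no new data are needed. The downside is that the composites are less specific than the components. For rare components such as vision and hearing they nearly repeat the death analysis, so those may stay descriptive only.
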